10.5 Other Safety Measures

10.5.1 Vital Signs

Vitals signs (blood pressure, pulse rate and respiration rate) will be summarized by study day for Days 1-14, including change from baseline.

In addition, vital signs data will be flagged as potentially clinically important (PCI) if they meet the CTCAE (v5.0) criteria for a Grade 3 or above event as shown in [Table 14](#).

Table 14 PCI Criteria for Vital Signs

Parameter	Units	PCI Criteria
Systolic Blood Pressure	mmHg	≥ 160
Diastolic Blood Pressure	mmHg	≥ 100

The number and percentage of participants showing shifts from baseline to worst-case post-baseline with respect to the PCI criteria will also be summarized for each parameter. Categories will be:

- Within range
- High

The determination of worst-case post-baseline will consider both scheduled (Day 4 and Day 7) and any unscheduled assessments which occur after the first dose of study treatment. Percentages will use the number of participants with at least one post-baseline assessment available. If the baseline value is missing it will be assumed to be within range for this summary.

All vital signs data will be listed, including flags for values which meet the PCI criteria. In addition, a separate listing of all vital signs assessments for any participant who meet has at least one value meeting the PCI criteria will be produced.

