10.4 Clinical Laboratory Evaluations

Local laboratory data will be used for all safety laboratory evaluations. Blood samples for safety laboratory evaluations will be collected at Baseline, Day 4 and Day 7. [Table 17](#) shows the parameters which will be collected and the units in which they will be supplied.

Laboratory data (hematology and chemistry parameters) will be summarized by treatment and visit. Changes from baseline at Day 4 and Day 7 will also be summarized.

Relative differentials (neutrophils, lymphocytes, monocytes, eosinophils and basophils) will be converted to absolute values as described in [Section 5.3.4.3](#).

The number and percentage of participants showing shifts from baseline to worst-case post-baseline with respect to the normal ranges will also be summarized for each parameter. Categories will be:

- Low
- Normal
- High

The determination of worst-case post-baseline will consider both scheduled (Day 4 and Day 7) and any unscheduled assessments which occur after the first dose of study treatment. Percentages will use the number of participants with at least one post-baseline assessment available. If the baseline value is missing it will be assumed to be normal for this summary. Worst-case can be either High or Low and if a participant has post-Baseline values both above and below the normal range then they will be counted in both relevant categories.

Safety laboratory values are also flagged for potentially clinically important (PCI) values if they meet any of the criteria for Grade 2 or higher events according to CTCAE V5.0 with the exception of lymphocytes where the lower limit for grade 3 is used as COVID-19 cases lymphopenia in most patients. The PCI criteria are listed in [Table 17](#). The number and percentage of participants showing shifts from baseline to worst-case post-baseline with respect to PCI criteria will be summarized for all parameters where PCI criteria have been defined. Categories will be:

- Low
- Within range
- High

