The determination of worst-case post-baseline will consider both scheduled (Day 4 and Day 7) and any unscheduled assessments which occur after the first dose of study treatment. Percentages will use the number of participants with at least one post-baseline assessment available. If the baseline value is missing it will be assumed to be within range for this summary. Worst-case can be either High or Low and if a participant has post-Baseline values both above and below the PCI criteria then they will be counted in both relevant categories.

Safety laboratory data will be listed by participant, including changes from baseline, normal ranges and flags for measurements outside the normal range and flags for meeting PCI criteria. In addition, for participants who meet at least one PCI criteria, all values within the laboratory type (hematology or clinical chemistry) will be listed separately.

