16.3 Safety

16.3.1 Tables

Number	Title	Population	Early Stop	Programming notes ¹
14.3.1.1.1	Summary of All TEAEs by System Organ Class and Preferred Term	Safety	Yes	DMC-Unblinded
14.3.1.1.2	Summary of Treatment Phase TEAEs by System Organ Class and Preferred Term	Safety	Yes	DMC-Unblinded
14.3.1.1.3	Summary of Follow-up Phase TEAEs by System Organ Class and Preferred Term	Safety	Yes	DMC-Unblinded
14.3.1.1.4	Summary of All TEAEs by Age Group, System Organ Class and Preferred Term	Safety		DMC-Safety Only produced if participants aged >65 are permitted to enter the study
14.3.1.2	Summary of Treatment-Related TEAEs by System Organ Class and Preferred Term	Safety	Yes	
14.3.2.1	Summary of Serious TEAEs by System Organ Class and Preferred Term	Safety	Yes	DMC-Unblinded
14.3.2.2	Summary of TEAEs Leading to Permanent Discontinuation from Study Drug by System Organ Class and Preferred Term	Safety	Yes	
14.3.2.3	Summary of TEAEs Leading to Withdrawal from the Study by System Organ Class and Preferred Term	Safety	Yes	
14.3.2.4	Summary of Fatal TEAEs by System Organ Class and Preferred Term	Safety	Yes	

Number	Title	Population	Early Stop	Programming notes ¹
14.3.2.5.1	Summary of TEAEs of Special Interest by Preferred Term and CTCAE Grade	Safety	Yes	DMC-Unblinded
14.3.2.5.2	Summary of TEAEs of Special Interest by Preferred Term and Relationship to Study Drug	Safety	Yes	DMC-Unblinded
14.3.4.1.1	Summary of Change from Baseline in Hematology	Safety	Yes	
14.3.4.1.2	Summary of Shifts from Baseline to Worst-case Post-Baseline with Respect to the Normal Range in Hematology	Safety	Yes	DMC-Unblinded
14.3.4.1.3	Summary of Shifts from Baseline to Worst-case Post-Baseline with Respect to the PCI Criteria in Hematology	Safety	Yes	DMC-Unblinded
14.3.4.1.4	Summary of Shifts from Baseline to Worst-case Post-Baseline with Respect to the PCI Criteria in Hematology, by Age Group	Safety		DMC-Safety Only produced if participants aged >65 are permitted to enter the study
14.3.4.2.1	Summary of Change from Baseline in Clinical Chemistry	Safety	Yes	
14.3.4.2.2	Summary of Shifts from Baseline to Worst-case Post-Baseline with Respect to the Normal Range in Clinical Chemistry	Safety	Yes	DMC-Unblinded
14.3.4.2.3	Summary of Shifts from Baseline to Worst-case Post-Baseline with Respect to the PCI Criteria in Clinical Chemistry	Safety	Yes	DMC-Unblinded

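### SAP 10.5.1 applies the laboratory days (Day 4 and Day 7) to vital signs scheduled daily, and every vital-signs output flagged for the DMC depends on high blood pressure alone

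*SAP*

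**What the plan says.** SAP 10.5.1 covers blood pressure, pulse rate and respiration rate. These "will be summarized by study day for Days 1-14, including change from baseline".

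It then sets a flagging rule: "vital signs data will be flagged as potentially clinically important (PCI) if they meet the CTCAE (v5.0) criteria for a Grade 3 or above event". Table 14, which carries out the rule, has two rows: systolic at or above 160 mmHg and diastolic at or above 100 mmHg. The shift categories are *Within range* and *High*; there is no *Low*, and no limit for pulse or respiration.

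On which readings count, the section says: "The determination of worst-case post-baseline will consider both scheduled (Day 4 and Day 7) and any unscheduled assessments which occur" after the first dose. It also plans "a separate listing of all vital signs assessments for any participant who meet has at least one value meeting the PCI criteria".

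SAP 10.4 uses the same days for laboratory data, where blood is taken at Baseline, Day 4 and Day 7. It has a normal-range shift (Low, Normal, High) as well as a PCI shift, and for the first it states: "Worst-case can be either High or Low and if a participant has post-Baseline values both above and below the normal range", the participant counts in both categories.

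SAP 7.4.5 says that the outputs expected for the DMC are those flagged in Appendix 1.

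**The concern.** Two things in this section do not fit their purpose.

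First, the worst-case rule appears to have been carried over from the laboratory section. The Schedule of Activities (Protocol 1.3) marks vital signs at Baseline and on each of Days 1 to 14. A worst case drawn from Day 4 and Day 7 is not the worst case of that series.

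Second, the vital-signs outputs that reach the DMC are all filtered through Table 14. In a hospitalized COVID-19 population, falling pressure, rising pulse and rising respiratory rate are readings a safety committee could reasonably want to see by arm. The protocol itself lists shock and arrhythmia among COVID-related complications (Protocol 2.1). In Table 14.3.5.2, *Within range* means only that no counted reading was high.

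At stake is the accuracy of one safety shift table (two if participants over 65 are admitted) and what the DMC sees during the trial.

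**Working it through.** The plan gives no figure to reproduce. The check compares schedules and counts outputs.

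**Step 1. Days used by the worst-case rule.**

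| | Vital signs | Safety laboratory |
|---|---|---|
| Scheduled after baseline | Days 1 to 14, daily (Protocol 1.3) | Day 4, Day 7 (SAP 10.4) |
| Summarized | Days 1 to 14 (SAP 10.5.1) | Day 4, Day 7 (SAP 10.4) |
| Scheduled days in the worst-case rule | Day 4, Day 7 | Day 4, Day 7 |

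- Laboratory: 2 of 2 scheduled days used.
- Vital signs: 2 of 14 used, so 14 − 2 = 12 are left out.
- If the Day 1 reading serves as baseline, as SAP 5.3.1.2 provides for an untimed Day 1 value, the count is 2 of 13, with 13 − 2 = 11 left out.
- Vital signs may stop at discharge (Protocol 1.3 footnotes). Read literally, a participant discharged before Day 4 contributes no scheduled reading to the shift.

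**Step 2. Limits in Table 14.** Four parameters (systolic, diastolic, pulse, respiration) in two directions give 4 × 2 = 8. Two have a limit (systolic high, diastolic high); 8 − 2 = 6 do not.

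**Step 3. Vital-signs outputs in SAP Appendix 1.**

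| Output | Content | Depends on Table 14 | DMC flag |
|---|---|---|---|
| Table 14.3.5.1 | Change from baseline | No | None |
| Table 14.3.5.2 | PCI shifts | Yes | DMC-Unblinded |
| Table 14.3.5.3 | PCI shifts by age group | Yes | DMC-Safety, only if participants over 65 are admitted |
| Listing 16.2.9.1 | All values | No | None |
| Listing 16.2.9.2 | Participants with a PCI value | Yes | DMC-Unblinded |

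Three of five are flagged, and 0 of those 3 are independent of Table 14.

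**Step 4. The laboratory comparison.** Appendix 1 has 12 laboratory outputs, 8 of them flagged for the DMC. Two of the 8 do not use PCI limits: "Summary of Shifts from Baseline to Worst-case Post-Baseline with Respect to the Normal Range in Hematology" (14.3.4.1.2) and "Summary of Shifts from Baseline to Worst-case Post-Baseline with Respect to the Normal Range in Clinical Chemistry" (14.3.4.2.2). Potassium has no low PCI limit in Table 17, yet a low potassium still reaches the DMC through the chemistry table. Vital signs have no such second view.

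**Step 5. Two illustrative participants.**

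- *High once, on Day 5.* Systolic is 160 mmHg at the scheduled Day 5 reading and below the limits otherwise. Day 5 is neither Day 4 nor Day 7 nor unscheduled, so Table 14.3.5.2 counts the participant as *Within range*. Listing 16.2.9.2 has no day restriction and includes the participant. Table and listing disagree.
- *Low only.* Systolic falls to 70 mmHg, with no reading at or above 160/100. The participant is *Within range* in Table 14.3.5.2 whichever days are used, and absent from Listing 16.2.9.2. The value is in Listing 16.2.9.1, which the DMC is not scheduled to receive.

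**The case against.** The case for leaving this alone has substance.

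- **DMC focus.** SAP 7.4.2 names severe and serious adverse events, gastrointestinal events and PCI laboratory data as the focus of safety review. Vital signs are not named, so a thinner package may be deliberate. This stands, and it lowers the weight of the second part.
- **Other routes.** Adverse event, serious adverse event and fatal event listings, concomitant-medication outputs (14.1.4.2, 16.2.4.7) and WHO OSCI outputs go to every meeting. The DMC can request unblinded data (Protocol 6.6.1). Protocol Appendix 3 counts clinically significant vital-sign changes as adverse events, apart from those due to the underlying disease unless more severe than expected. This largely stands. What these routes can miss is a low or fast reading that is neither treated nor reported; non-serious, non-gastrointestinal events below Grade 3 stay in the medical notes (Protocol 8.3).
- **The charter.** SAP 7.4.6 refers to a DMC charter that is not among the documents and may add outputs. This stands; the point concerns only the package flagged in Appendix 1.
- **One-sided limits are common, and the label is qualified.** In Table 17, 7 of the 10 laboratory parameters with a limit have it on one side only, and the vital-signs table says that it is relative to the PCI criteria. Both are true. The label still reads more broadly than its content.
- **No normal ranges.** The SAP gives none for vital signs, which explains why there is no normal-range shift table. It does not explain why the two outputs needing no threshold are unflagged.

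None of this answers the Day 4 and Day 7 wording, which conflicts with the schedule and with the daily summary in the same section.

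A reader might infer that the DMC cannot see hypotension or tachycardia at all. The documents do not support that, given the routes above. Nor do they show that Table 14 breaks the plan's own CTCAE rule: the CTCAE text is not reproduced in them.

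**Conclusion.** The point holds and is minor.

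The firmer part is the worst-case rule. As written, Tables 14.3.5.2 and 14.3.5.3 leave out 12 of 14 scheduled days (11 of 13 if Day 1 is the baseline) and can understate even high pressures. This rests on a literal reading; a programmer might use all days regardless, but the text does not say so. It does not follow that the DMC would miss those high pressures altogether, because Listing 16.2.9.2 takes any qualifying value.

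The second part is reduced visibility: 0 of 3 DMC-flagged vital-signs outputs are independent of Table 14. It assumes that the package is what Appendix 1 flags and that vital signs means the parameters in SAP 10.5.1. Temperature and oxygen saturation are reported as efficacy data and go to the DMC only at the 60-participant meeting.

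A reader might also infer that low readings are hidden from the final report. They are not: Table 14.3.5.1 gives minimum and maximum by day and arm, and Listing 16.2.9.1 gives every value. No endpoint or efficacy estimate changes. The number of participants affected cannot be computed, since the documents give no low-pressure limit and no event rate.

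**What to change.** 1. In SAP 10.5.1, replace the reference to Day 4 and Day 7 with all scheduled post-baseline days to Day 14 plus unscheduled assessments.
2. In Appendix 1, flag Table 14.3.5.1 and Listing 16.2.9.1 as DMC-Unblinded. Flagged outputs independent of Table 14 go from 0 of 3 to 2 of 5, with no new threshold.
3. In the vital-signs PCI shift, relabel *Within range* as *Not high*.

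Optional, for the medical monitor to decide: low limits for systolic and diastolic pressure and high limits for pulse and respiration. If these are added, include a *Low* category, count a participant in both directions as SAP 10.4 does, and keep the CTCAE Grade 3 wording only for limits taken from it. The documents give no values for these limits, so they are not part of the required change.

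The cost is a text edit, a label edit, two flags and a few lines of programming; the data are already collected. The downside is a longer DMC package and, if limits are added, more flags caused by COVID-19 itself in both arms. The change mainly helps inpatient days, since vital signs may not be taken after discharge.

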*If a patient is discharged then these assessments may not be performed.

@Whilst an inpatient, participants should have a daily assessment for evidence of nausea, vomiting, diarrhoea, bloating and abdominal pain. This information will be collected for outpatients in the patient questionnaire.

& If a participant is not discharged at Day 14 and remains in hospital, Day 14 assessments will be performed until a participant is discharged from hospital or they reach the final follow-up visit (Day 42).

¹ Pregnancy test will only be performed in women of child-bearing potential (Appendix 2).

² If the patient is on 3L/min oxygen flow or less, this assessment should be performed after the patient is at rest on room air for 10 minutes, as detailed in section 8.1.1.

³ If the patient is discharged prior to these blood tests, where possible outpatient blood testing will be organised.

⁴ Extraction of relevant clinical data from the patient's medical record (such as but not limited to symptoms, concomitant medications, other relevant blood tests, and radiology reports such as chest radiograph or CT scan).

⁵ If the patient is discharged, they will be given a daily questionnaire to complete; a telephone call will be made on day 7, 14, 21 and 42 (telephone call has a window of +/- 1 day).

⁶ The patient will be asked to continue to fill the questionnaire daily until their symptoms have fully resolved for 48 hours or until the day 42 telephone visit (whichever is earlier).

⁷ This is an optional sample for research purposes but will be collected whenever possible once at the Baseline visit and then again once between Days 5-14. If the patient is discharged prior to this faecal test, where possible, an outpatient sample will be collected.

⁸ Administered twice daily for six doses) and then once daily for the remaining days (17 doses total). Treatment will be stopped if the participant is admitted to ICU, meets individual stopping criteria, or is withdrawn from the study.

⁹ Smoking status to include whether current-smoker, ex-smoker, or never-smoker; and to quantify current usage and total pack-year history.

2. Introduction

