5.3.1.2 Baseline

The last non-missing value collected before first study dose will be taken as the baseline measurement for all parameters. If data is collected on Day 1 without an associated time being provided, it will be assumed to be pre-dose.

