14.3.4.2.4	Summary of Shifts from Baseline to Worst-case Post-Baseline with Respect to the PCI Criteria in Clinical Chemistry, by Age Group	Safety		DMC-Safety Only produced if participants aged >65 are permitted to enter the study
14.3.5.1	Summary of Change from Baseline in Vital Signs	Safety	Yes	
14.3.5.2	Summary of Shifts from Baseline to Worst-case Post-Baseline with Respect to the PCI Criteria in Vital Signs	Safety	Yes	DMC-Unblinded

Number	Title	Population	Early Stop	Programming notes ¹
14.3.5.3	Summary of Shifts from Baseline to Worst-case Post-Baseline with Respect to the PCI Criteria in Vital Signs, by Age Group	Safety		DMC-Safety Only produced if participants aged >65 are permitted to enter the study

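### The vital-signs worst-case rule in SAP 10.5.1 takes scheduled readings from Days 4 and 7 only (plus unscheduled ones), although vital signs are scheduled daily to Day 14, so the blood-pressure shift tables can undercount participants with PCI values

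*SAP*

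**What the plan says.** SAP 10.5.1 (Vital Signs) sets the readings that can enter the shift table: "The determination of worst-case post-baseline will consider both scheduled (Day 4 and Day 7) and any unscheduled assessments which occur after the first dose". The same section says that blood pressure, pulse and respiration rate "will be summarized by study day for Days 1-14, including change from baseline". The Schedule of Activities in Protocol 1.3 marks vital signs at baseline and on each day from Day 1 to Day 14 or the day of discharge. A footnote limits this: "If a patient is discharged then these assessments may not be performed".

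The worst-case sentence stands in identical words, twice, in SAP 10.4 (Clinical Laboratory Evaluations). There it fits, because "Blood samples for safety laboratory evaluations will be collected at Baseline, Day 4 and Day 7".

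The output is a count of people: "The number and percentage of participants showing shifts from baseline to worst-case post-baseline with respect to the PCI criteria will also be summarized". The denominator has no day restriction: "Percentages will use the number of participants with at least one post-baseline assessment available". PCI criteria exist for two parameters only (SAP Table 14): systolic pressure of 160 mmHg or more and diastolic pressure of 100 mmHg or more.

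SAP 16.3.1 lists the result as Table 14.3.5.2, "Summary of Shifts from Baseline to Worst-case Post-Baseline with Respect to the PCI Criteria in Vital Signs". It is marked for unblinded delivery at all DMC meetings, and SAP 16 makes every listed output part of the final analysis. Table 14.3.5.3 repeats it by age group if participants over 65 are admitted.

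**The concern.** A scheduled reading on Day 2 or Day 9 is neither a Day 4 or Day 7 reading nor an unscheduled one, so the rule as written gives it no way into the shift table. A participant whose only PCI pressures fall on such days would be shown as within range. The omitted days include Days 1-3, when most participants are dosed twice daily (SAP 5.3.2.7).

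Numerator and denominator also follow different rules. A participant discharged by Day 3 stays in the denominator through any post-baseline reading, yet can enter the numerator only through an unscheduled one.

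The table matters because it is the only tabulation of the SAP 10.5.1 vital signs that goes to every DMC meeting. The change-from-baseline summary, Table 14.3.5.1, carries no DMC mark. The same undercount would pass into the final report.

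**Working it through.** The plan states no figure for this point, so there is none to reproduce. The check compares the schedules, counts days, and then asks how many affected participants would be missed.

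**1. Schedules side by side**

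- Laboratory (SAP 10.4): post-baseline samples on Days 4 and 7. The rule names 2 of 2 scheduled days.
- Vital signs (Protocol 1.3): 15 marks in the row, which are baseline, Days 1-13, and Day 14 or discharge. That is 14 days after the baseline column. The rule names 2 of 14.
- SAP 5.3.1.2 can remove one of the 14: "If data is collected on Day 1 without an associated time being provided, it will be assumed to be pre-dose". That leaves 13.

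**2. Scheduled days left out**

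- In hospital to Day 14: 14 − 2 = 12, and 12/14 = 85.7%.
- The same, with Day 1 as baseline: 13 − 2 = 11, and 11/13 = 84.6%.
- Last inpatient day is Day 7: 7 − 2 = 5, and 5/7 = 71.4%.
- Last inpatient day is Day 3: no scheduled reading counts.

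**3. Share of affected participants missed**

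The table counts participants, so the share of days left out is not the share of people missed. The documents say nothing on how often or how long PCI pressures occur. The patterns below are assumptions. All take a participant in hospital to Day 14, 14 post-baseline days and no unscheduled readings.

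*(a) One run of r consecutive abnormal days, placed uniformly.* There are 15 − r possible starts. A run is missed if it contains neither Day 4 nor Day 7.

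| r (days) | Starts | Starts missed | Share missed |
|---|---|---|---|
| 1 | 14 | 12 | 86% |
| 2 | 13 | 9 | 69% |
| 3 | 12 | 6 | 50% |
| 5 | 10 | 3 | 30% |
| 7 | 8 | 1 | 12.5% |
| 8 or more | 15 − r | 0 | 0% |

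The last row holds because 8 or more consecutive days within Days 1-14 must include Day 7.

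*(b) k abnormal days scattered at random.* Share missed = C(12,k)/C(14,k): 86% for k = 1, 73% for k = 2, 60% for k = 3, 40% for k = 5.

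*(c) Independent days, each abnormal with probability p.* Share missed = 1 − [1 − (1 − p)²]/[1 − (1 − p)¹⁴]: 81% at p = 0.05, 75% at 0.10, 62% at 0.20, 49% at 0.30, 25% at 0.50.

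*(d) Days correlated within participant (beta-binomial, p = 0.10).* Share missed: 59% at correlation 0.3, 49% at 0.5, 36% at 0.7, 16% at 0.9.

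The range is therefore 0% to about 86%, and persistence decides where in it the truth lies. Any unscheduled PCI reading lowers the share missed.

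**The case against.** A reader might infer that the DMC's vital-signs table misses most abnormal readings and so hides a safety difference between arms. The documents do not support that, for four reasons.

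- **The DMC has another source.** SAP 10.5.1 also requires a separate listing of every vital-signs assessment for any participant with at least one PCI value, with no limit to Days 4 and 7. It is listing 16.2.9.2, marked for unblinded delivery at all DMC meetings. A participant with a high value on Day 2 only would appear there.
- **Unscheduled post-dose readings count**, and a participant with persistent elevation is captured once if either named day is high. A majority missed is one assumption among several.
- **The scope is narrow.** Pulse and respiration have no PCI criteria, so they are outside this table under any rule. SAP 7.4.2 does not name vital signs in the stated focus of the DMC safety review.
- **There is a further route.** Adverse events of Grade 3 or 4 are recorded in the CRF, and the table of all treatment-emergent events goes to every meeting.

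All of this stands, and it limits the harm. It does not make the rule right. Listing 16.2.9.2 could show a participant for a Day 9 value while Table 14.3.5.2 in the same package shows that participant as within range. Arm-level counts would have to be rebuilt by hand.

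**Conclusion.** The rule is wrong as written and should be corrected. It conflicts with the protocol's daily schedule and with the Days 1-14 summary in its own section, and no reason for the restriction is given. That the sentence was carried over from the laboratory section is a fair inference from the identical wording, but the documents do not say so.

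What is established without assumptions is that, for a participant in hospital to Day 14, the rule excludes 12 of 14 scheduled days (or 11 of 13). How many participants are misclassified cannot be known from the documents. The 0% to 86% range rests on the assumed patterns, on a stay to Day 14 and on no unscheduled readings. A participant discharged by Day 3 with a scheduled PCI value would always be missed.

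This is a reporting error in one descriptive safety table and its by-age repeat. It has no bearing on sample size, efficacy inference or the study stopping criteria. A claim that an arm difference would be concealed from the DMC goes beyond the documents, given listing 16.2.9.2.

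**What to change.** In SAP 10.5.1, replace the parenthesis naming Days 4 and 7 so that the worst case is taken over *all scheduled post-first-dose assessments (Days 1-14 and any later inpatient assessments)*, and keep the unscheduled assessments. The later inpatient readings arise because Protocol 1.3 continues the Day 14 assessments for participants still in hospital, up to Day 42. Apply the change to Tables 14.3.5.2 and 14.3.5.3. Leave the sentence in SAP 10.4 as it is, since it matches the laboratory schedule. The PCI thresholds are not changed.

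The numerator and denominator then draw on the same readings, and the tables agree with listing 16.2.9.2. The cost is one SAP line and one selection condition in the program, using data already scheduled for collection. The documents do not show whether any DMC package has been produced. If one has, its version of the table should be read with this limitation in mind.
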